## **11. Human research protection**

### *11.1 Data confidentiality*

Paper-based records will be kept in a secure location and only be accessible to personnel involved in the study. Computer-based files will only be made available to personnel involved in the study through the use of access privileges and passwords. Wherever feasible, identifiers will be removed from study-related information. Precautions are in place to ensure the data are secure by using passwords and encryption, because the research involves web-based surveys.

### *11.2 Subject confidentiality*

Research material will be obtained from participant surveys and wearable devices. All participants will provide informed consent for access to these materials. The data to be collected include data on participant characteristics and behaviors, step counts, and sleep patterns. Research material that is obtained will be used for research purposes only. The same procedure used for the analysis of automated data sources to ensure protection of patient information will be used for the survey data, in that patient identifiers will be used only for linkage purposes or to contact patients. The study identification number, and not other identifying information, will be used on all data collection instruments. All study staff will be reminded to appreciate the confidential nature of the data collected and contained in these databases. The Penn Medicine Academic Computing Services (PMACS) will be the hub for the hardware and database infrastructure that will support the project and is where the Way to Health web portal is based. The PMACS is a joint effort of the University of Pennsylvania's Abramson Cancer Center, the Cardiovascular Institute, the Department of Pathology, and the Leonard Davis Institute. The PMACS provides a secure computing environment for a large volume of highly sensitive data, including clinical, genetic, socioeconomic, and financial information. Among the IT projects currently managed by PMACS are: (1) the capture and organization of complex, longitudinal clinical data via web and clinical applications portals from cancer patients enrolled in clinical trials; (2) the integration of genetic array databases and clinical data obtained from patients with cardiovascular disease; (3) computational biology and cytometry database management and analyses; (4) economic and health policy research using Medicare claims from over 40 million Medicare beneficiaries. PMACS requires all users of data or applications on PMACS servers to complete a PMACS-hosted cybersecurity awareness course annually, which stresses federal data security policies under data use agreements with the university. The curriculum includes Health Insurance Portability and Accountability Act (HIPAA) training and covers secure data transfer, passwords, computer security habits and knowledge of what constitutes misuse or inappropriate use of the server. We will implement multiple, redundant protective measures to guarantee the privacy and security of the participant data. All investigators and research staff with direct access

to the identifiable data will be required to undergo annual responsible conduct of research, cybersecurity, and HIPAA certification in accordance with University of Pennsylvania regulations.

Data will be stored, managed, and analyzed on a secure, encrypted server behind the University of Pennsylvania Health System (UPHS) firewall. This server was created for projects conducted by the Penn Medicine Nudge Unit related to physician and patient behavior at UPHS. All study personnel that will use this data are listed on the IRB application and have completed training in HIPAA standards and the CITI human subjects research. Data access will be password protected. Whenever possible, data will be deidentified for analysis.

### *11.3 Subject privacy*

Interested participants will be directed to the Way to Health portal where they will be asked to enter data related to eligibility and their demographic characteristics. Enrollment will include a description of the voluntary nature of participation, the study procedures, risks and potential benefits in detail. The enrollment procedure will provide the opportunity for potential participants to ask questions and review the consent form information with family and friends prior to making a decision to participate. Participants will be told that they do not have to answer any questions if they do not wish and can drop out of the study at any time, without affecting their medical care or the cost of their care. They will be told that they may or may not benefit directly from the study and that all information will be kept strictly confidential, except as required by law. Subjects will have access to a copy of the consent document. All efforts will be made by study staff to ensure subject privacy.

### *11.4 Data disclosure*

The following entities, besides the members of the research team, may receive protected health information (PHI) for this research study: Wells Fargo, the company which processes study-related payments. Patient addresses and account balances will be stored on their secure computers. Nokia, the company that designs and manufactures the wearable devices used in the study to track participant physical activity. Twilio, Inc., the company which processes some study-related messages. Twilio will store patients' phone numbers on their secure computers. Qualtrics, Inc., the company which processes most study-related surveys. Qualtrics will house de-identified answers to these surveys on their secure servers. The Office of Human Research Protections at the University of Pennsylvania -Federal and state agencies (for example, the Department of Health and Human Services, the National Institutes of Health, and/or the Office for Human Research Protections), or other domestic or foreign government bodies if required by law and/or necessary for oversight purposes.

### *11.5 Data safety and monitoring*

The Principal Investigator will be responsible for monitoring the study. All participants will be given anticipatory guidance on when to seek medical attention. In addition, participants will be asked to report to the study team any injuries or medical care that they feel resulted from participation in the study. They can either call the study team or send an email. The research coordinator will call the participant to collect information regarding the issue and then the PI will review and determine whether it is ok to proceed, further investigation is needed, or the participant should stop the study. For this study there will be no stopping rules or endpoints and thus no planned interim analyses.

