### **--Randomization—**

Participants are considered ready to be randomized once they have completed all surveys, established a baseline step count, and selected a step goal increase.

Participants will be stratified on baseline step count (less than 5000 steps, 5001 to 7500 steps, or more than 7500 steps). Participants will then be randomly assigned within their strata in blocks of four groups, with each group having 3 participants. The first participant in the group will be randomly assigned to the arm and the next 2 participants will be assigned to fill that group. Then the next participant will be randomly assigned to an arm within that block and the following two participants will be assigned to fill that group, and so on until the block within the strata is filled of 4 groups, each with three participants per group.

Participants in all arms will be asked to complete a series of follow-up surveys the end of the 24-week intervention period and again at the end of the 12-week follow up period. The interventions within each arm are as follows:

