### **--Arm 1: Control—**

Participants in this arm will receive no other interventions during the 24-week intervention period or the 12-week follow-up period.

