### **--Arm 2-4: social incentive-based gamification interventions--**

Participants randomized to the one of the three intervention arms will have a 4-week ramp up towards their step goal (the “ramp-up period). The net difference between baseline and their goal will be divided by 4 and the participant will be asked to achieve the 25% increase each week for the 4-week ramp-up and then maintain the step goal for the remaining study period. For example, a participant with a baseline of 6000 steps and goal of 8000 steps will be asked to achieve goals of 6500, 7000, 7500, and 8000 for each of the first four weeks of the study. The participant will be asked to maintain their goal (e.g. 8000 steps per day) during the 20-week “maintenance period” and the 12-week “follow-up period”

Participants in arms 2-4 will be entered into an intervention approach that has points and levels designed to incorporate insights from behavioral economics. First, participants will be asked to sign a pre-commitment pledge to strive to achieve their step goal during the 36-week study. Pre-commitment has been demonstrated to motivate behavior change. Second, at the beginning of each week the participant receives 70 points (10 for each day that week). If the participant does not achieve their step goal, they lose 10 points from their balance. This leverages loss aversion, which has been demonstrated to motivate behavior change more effectively with losses than gains. Third, at the end of each week if the participant has at least 40 points, he or she will move up a level (levels from lowest to highest: blue, bronze, silver, gold, platinum). If not, participants will drop a level. All participants begin at the silver level. Each week, participants get a fresh set of 70 points on Monday.

At 8 and 16 weeks, participants struggling to meet their goals (defined as in the blue or bronze levels of the game) will be contacted to inquire about their progress in the study. They will be reset to the silver level and given the opportunity to readjust their goals among the initial options.

Weekly feedback will differ among the three arms to induce the different social incentives (support, competition, and collaboration) as follows:

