## *11.6 Risk/benefit*

### *11.6.1 Potential study risks*

To minimize the chance for serious and unexpected adverse events, study participants will be screened through exclusion criteria for any health conditions that may be exacerbated by participating in a physical activity study. The program will use a gradual increase in physical activity during the first month that should pose little health risk to participants. Participants are given guidance on when to seek medical attention and a reporting protocol is in place to capture any changes in symptoms with physical activity. Another potential risk of this study is a breach of participant confidentiality. We will minimize this risk by using secure data methods as described previously. Due to the financial incentives in this study, we will be collecting social security numbers so that we can complete W-9 forms for participants. Social security numbers only will be used to generate W-9 forms and will be deleted once they are no longer needed. We will also collect home addresses to mail incentive payments. This will be done through a University of Pennsylvania approved partnership with Wells Fargo. Accidental disclosure of social security numbers could lead to identity theft. We will use commercial-grade encryption to protect social security information in transit. Names and addresses will be stored in encrypted databases. These data will be viewable only by the respective participants, the study coordinator(s) and the project manager(s). All other members of the research team will be able to view only participant ID numbers. Even the study arms will be identified by code letters until both the statistician and PI agree that analysis is complete.

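### The only harms collection described is self-initiated reporting of events that participants attribute to the study, so capture is likely to be incomplete and may differ by arm

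*Combined protocol and SAP*

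**What the plan says.** Section 11.5 sets out the reporting route. After general guidance on seeking care, "participants will be asked to report to the study team any injuries or medical care that they feel resulted from participation in the study". The channel is the participant's own contact: "They can either call the study team or send an email". Staff act after that: "The research coordinator will call the participant to collect information regarding the issue", and the principal investigator then reviews the case.

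Section 11.6.1 describes the system more broadly: "a reporting protocol is in place to capture any changes in symptoms with physical activity". It gives no procedure beyond the one in section 11.5.

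After randomization, section 5.1 describes one kind of staff-initiated contact. In arms 2-4, at weeks 8 and 16, "participants struggling to meet their goals (defined as in the blue or bronze levels of the game) will be contacted to inquire about their progress". Control has no levels, and its entry reads: "Participants in this arm will receive no other interventions during the 24-week intervention period or the 12-week follow-up period".

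One contact point is common to everyone. "Participants in all arms will be asked to complete a series of follow-up surveys", once at the end of week 24 and again at the end of follow-up (week 36). The instruments that section 5.1 names for months 0 and 6 cover health status (EQ-5D-5L), exercise self-efficacy, eating, sleep, mood, social support and qualitative feedback. The contents of the follow-up surveys are not otherwise itemised.

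Sections 3 and 9 contain no harms outcome, harms denominator or harms analysis.

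**The concern.** Two filters stand between an injury and the study record. The participant must believe that the study caused it, and must then take the trouble to call or write. Events that fail either filter are not seen through this route, in any arm.

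The filters may also work differently by arm. Arms 2-4 have a pledge, weekly ramp-up targets, points and levels, so a sore knee is easily linked to the programme. Controls have less to link it to. In addition, an injury that stops someone walking can itself lower their game level and so prompt a week 8 or 16 contact in arms 2-4. An equally injured control has no corresponding contact.

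What is at stake is any statement about safety made from the trial's data. If the team reports few injuries, or more injuries under one intervention than under control, the reader could not separate true risk from the way events came to light.

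**Working it through.** **1. The plan's own figure.** No harms figure is stated. The only design figure needed is the arm size: 600 participants allocated 1:1:1:1 gives 600 / 4 = 150 per arm (section 5.4). That total reproduces from the stated inputs (800-step difference, SD 2000, two-sided alpha 0.017, 80% power, 10% dropout):
- n per arm = 2 × (2.387 + 0.842)² × (2000/800)², which rounds up to 131.
- Allowing for dropout, 131 / 0.90 rounds up to 146, and 4 × 146 = 584, against the stated 600.
- With 150 × 0.90 = 135 evaluable per arm, power is 0.816.

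The harms point does not depend on this calculation.

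**2. The passages side by side.**

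| Feature | Control | Arms 2-4 |
|---|---|---|
| Instruction to report events attributed to the study | yes | yes |
| Phone or email route | yes | yes |
| Device and goal choice before randomization | yes | yes |
| Pledge, ramp-up, points, levels | no | yes |
| Staff contact at weeks 8 and 16 | none described | blue or bronze level only, about progress |
| Surveys at weeks 24 and 36 | yes | yes |
| Injury or medical-care item listed | no | no |

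The instruction is the same in every arm. What may differ is how readily an event is attributed to the study, and whether staff make contact.

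**3. Illustration.** The documents give no injury rate or reporting rate, so every risk and capture value below is an assumption. Expected reported events = n × true risk × capture probability. When true risk is equal, it cancels and the apparent ratio equals the ratio of capture probabilities.

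With n = 150 and true risk 10% in every arm, there are 15 true injuries per arm:
- Capture 30% everywhere: 15 × 0.30 = 4.5 reported, ratio 1.0, and 10.5 of 15 (70%) missed.
- Capture 30% in control and 45% in an intervention arm: 4.5 against 6.75, ratio 1.5.
- Capture 30% in control and 60% in an intervention arm: 4.5 against 9.0, ratio 2.0.

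Now suppose that only the week 8 and 16 contact raises capture. Let f be the share of injured intervention participants who are contacted. Intervention capture = (1 − f) × 0.30 + f × (capture if contacted).
- f = 0.10, capture if contacted 0.60: 0.27 + 0.06 = 0.33, ratio 0.33 / 0.30 = 1.1.
- f = 0.40, capture if contacted 0.90: 0.18 + 0.36 = 0.54, ratio 0.54 / 0.30 = 1.8.

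These figures show direction and sensitivity. They are not estimates for this trial.

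**The case against.** The strongest reply is that the plan makes no between-arm harms comparison. Section 11.5 is a case-handling procedure: a report, a call, a review. This is correct, and it confines the point to safety statements drawn from the trial.

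Several stronger readings are tempting but are not supported:

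- A reader might infer that the low-risk assessment in section 11.6.3 rests on these reports. It is a forward-looking expectation based on the exclusion criteria, with the gradual increase cited in section 11.6.1. It does not use injury counts from the trial.
- A reader might infer that controls have nothing to attribute an injury to. They also wear the tracker in the run-in and choose a higher goal before randomization. Lower attribution in control is plausible, not established.
- A reader might infer that everyone in arms 2-4 gets extra contact. Only blue or bronze participants do, at two time points, and the stated topic is progress, not injury.
- A reader might infer that every goal in the programme is at least 33% above baseline. The option of 1500 steps above baseline is 1500 / 6000 = 25% for a participant starting at 6000.
- A reader might infer a flat contradiction between sections 11.5 and 11.6.1. The latter speaks of symptoms with physical activity, which narrows the gap. What remains is symptoms on one side, and injuries or medical care attributed to the study on the other.

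It is also fair to say that the follow-up surveys are not fully itemised and include free-text feedback. An injury item could exist unlisted, and some events may surface there anyway. Those possibilities soften the point. They do not supply a uniform, solicited question in every arm.

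**Conclusion.** The point holds as a minor and inexpensive improvement. The only harms procedure described depends on the participant's own attribution and initiative, and it is narrower than section 11.6.1 suggests. Capture is likely to be incomplete in every arm and may differ between control and arms 2-4.

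Neither the size nor the existence of a between-arm bias can be established from the documents. The illustrative ratios run from 1.0 to 2.0 purely according to the assumed capture probabilities. Even with equal capture, events are lost whenever capture is below 100%. The conclusion also assumes that the follow-up surveys contain no unlisted injury item.

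The primary step-count analysis, the sample size and the error control are unaffected.

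**What to change.** Keep the phone and email route and the existing review of reports unchanged. Then:

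1. Add one fixed question to the week-24 and week-36 surveys, identical in all four arms, on any injury or medical care whatever its perceived cause. At week 24 the period is since randomization; at week 36 it is since the previous survey.
2. Report counts by arm from those answers, with the number of survey responders in each arm as the denominator.
3. List separately the spontaneous reports and any event first learned of at a week 8 or 16 contact.
4. Align the description in section 11.6.1 with what is actually collected.

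The cost is one or two items in surveys that already exist, and one table. There are downsides. The surveys become slightly longer and more unrelated events are counted. Participants must recall 24 weeks at the first survey and 12 at the second. Survey non-response may itself differ by arm and could miss people who left because of an injury. Showing responders by arm next to the counts makes that last limit visible.

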## *11.6 Risk/benefit*

### *11.6.1 Potential study risks*

To minimize the chance for serious and unexpected adverse events, study participants will be screened through exclusion criteria for any health conditions that may be exacerbated by participating in a physical activity study. The program will use a gradual increase in physical activity during the first month that should pose little health risk to participants. Participants are given guidance on when to seek medical attention and a reporting protocol is in place to capture any changes in symptoms with physical activity. Another potential risk of this study is a breach of participant confidentiality. We will minimize this risk by using secure data methods as described previously. Due to the financial incentives in this study, we will be collecting social security numbers so that we can complete W-9 forms for participants. Social security numbers only will be used to generate W-9 forms and will be deleted once they are no longer needed. We will also collect home addresses to mail incentive payments. This will be done through a University of Pennsylvania approved partnership with Wells Fargo. Accidental disclosure of social security numbers could lead to identity theft. We will use commercial-grade encryption to protect social security information in transit. Names and addresses will be stored in encrypted databases. These data will be viewable only by the respective participants, the study coordinator(s) and the project manager(s). All other members of the research team will be able to view only participant ID numbers. Even the study arms will be identified by code letters until both the statistician and PI agree that analysis is complete.

### *11.6.2 Potential study benefits*

Through participation in this study, each participant will have the potential to increase physical activity which could improve their health and reduce their risk for future disease. If this approach is effective, it could have tremendous benefits for society if adopted on a wide scale to help individuals. It is expected that other people will gain knowledge from this study and that participation could help understand how to effectively motivate individuals to change behavior. Participants may also receive no benefit from their participation in the study.

### *11.6.3 Risk/benefit assessment*

Anticipated risks of this study should be minimal and the risk/benefit ratio is very favorable. To minimize the chance for serious and unexpected adverse events, study participants will be screened through exclusion criteria for any health conditions that may be exacerbated by participating in this study. We have previously outlined the procedures that will be used to prevent a breach of participant data.
